1.1. Primary Objective and Endpoint

1.1.1. To determine the time to first subsequent therapy.

1.1.1.1 Endpoint: The time from completion of platinum-based therapy for treatment of recurrence until initiation of post-olaparib treatment, for delayed start olaparib in platinum sensitive recurrent epithelial ovarian cancer with a complete or partial response to last platinum therapy

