5. SURVEILLANCE MONITORING PLAN

This is a single-arm, open-label phase II clinical trial evaluating delayed start olaparib maintenance therapy, based on a rise in CA125, for patients with epithelial ovarian cancer who have had a partial or complete response to platinum-based treatment. Patients will be enrolled within 8 weeks of completing platinum-based therapy for recurrent disease. At the time of enrollment, patients will be monitored with CA125 levels every 28 days.

At the first evidence of a two-fold rise in CA125 from baseline, patients will undergo a CT scan to evaluate for any visible lesions, including new lesions for those with CR and new, persistent or progressive lesions for those with PR to most recent therapy, and then will be started on olaparib therapy. In the setting of new or progressive lesions, patients will be followed per protocol. Patients may undergo CT imaging prior to rise in CA-125 at the discretion of the treating physician for patient symptoms. Eighty-one patients will be enrolled through UPMC medical and gynecologic oncology offices.

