6.1. Agent Administration

Olaparib treatment will be started when CA125 rises by two-fold of their nadir value. Olaparib will be dosed at 300 mg orally twice a day. Twenty-eight days of treatment will be considered one cycle. Patients will be required to maintain a medication diary (See Appendix B).

Patients starting olaparib will continue treatment until disease progression, per RECIST v1.1³⁹ or intolerable toxicity, defined as any grade 3 or 4 adverse event, per National Cancer Institute's Common Terminology Criteria for Adverse Events (CTCAE) v5.0 or Patient Reported Outcomes-Common Terminology Criteria for Adverse Events (PRO-CTCAE), that does not resolve completely or to grade 1 within 28 days after onset. Patients removed from study for unacceptable adverse event(s) will be followed closely until resolution or stabilization of the adverse event (at least 30 days).

Olaparib is FDA-approved for maintenance therapy for patients with platinum sensitive recurrent epithelial ovarian cancer with a complete or partial response to most recent platinum based chemotherapy. Therefore, drug will be covered by standard insurance. Additionally, after discussion with The UPMC Health Plan, they will approve treatment after 2 prior lines even with the delay in standard start time defined by the maintenance indication.

Treatment will be administered on an outpatient basis. Appropriate dose modifications are described in Section 7. No other investigational or commercial agents or therapies may be administered with the intent to treat the patient's malignancy.

Reported adverse events and potential risks are described in Section 7.

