6.2. General Concomitant Medication and Supportive Care Guidelines

6.2.1. Concomitant Therapy:

Patients must be instructed not to take any additional medications (including over-the-counter products) during the trial without prior consultation with the investigator. The investigator should instruct the patient to notify the study site about any new medications he/she takes after the start of study drug. All medications (other than study drug) and significant non-drug therapies (including physical therapy and blood transfusions) taken within 28 days of starting study treatment through the 30-day safety follow up visit should be reported on the Case Report Form. If concomitant therapy must be added or changed, the reason and name of the drug/therapy will be recorded.

In general, the use of any concomitant medication/therapies deemed necessary for the care of the patient are allowed, including drugs given prophylactically (e.g. antiemetics +/- steroids), with the following exceptions:

- No other investigational therapy will be given to patients.
- No anticancer agents other than the study medication administered as part of this study protocol should be given to patients. If such agents are required for a patient then the patient must first be withdrawn from the study.
- Leukocyte growth factors (e.g., G-CSF and GM-CSF) are not to be administered systematically but may be prescribed by the investigator for severe neutropenia if this is thought to be appropriate.
- No live vaccines will be administered to patient due to immunosuppressant potential of olaparib.

Drugs or substances known to be inhibitors or inducers of the isoenzyme CYP3A should be avoided in association with olaparib as these can alter drug metabolism. Strong inhibitors or inducers of the isoenzyme CYP3A should not be administered as systemic therapy and should be avoided whenever possible (See Appendix C). Investigators should consult a frequently updated drug information reference for a list of strong inducers and inhibitors.

- **CYP3A inhibitors:** Avoid concomitant use with moderate or strong CYP3A inhibitors (consider alternative agents with less CYP3A inhibition). If co-administration with a **moderate** CYP3A inhibitor cannot be avoided, reduce dose to 150 mg twice daily. If co-administration with a **strong** CYP3A inhibitor cannot be avoided, reduce dose to 100 mg twice daily.

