12.1.1. Definitions

Evaluable for toxicity. All patients will be evaluable for toxicity from the time of their first treatment with olaparib.

Evaluable for objective response by RECIST. Patients who have received at least 1 cycle of therapy and have had their disease re-evaluated with a 3-month post treatment CT will be considered evaluable for response. These patients will have their response classified according to the definitions stated below. (Note: Patients who exhibit objective disease progression prior to the end of cycle 1 will also be considered evaluable.)

Evaluable for objective response by CA-125. Patients who have received at least 1 cycle of therapy, have a CA-125 before treatment below the upper limit of the normal (for values above this limit, any increase in a second sample has to be <15% increase) and have had their disease re-evaluated with monthly CA125, will be considered evaluable for response. These patients will have their response classified according to the definitions stated below. (Note: Patients who exhibit objective disease progression prior to the end of cycle 1 will also be considered evaluable.)

Evaluable Non-Target Disease Response. Patients who have lesions present at baseline that are evaluable but do not meet the definitions of measurable disease, have received at least one cycle of therapy, and have had their disease re-evaluated, will be considered evaluable for non-target disease. The response assessment is based on the presence, absence, or unequivocal progression of the lesions.

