13.3 DATA ANALYSIS

13.3.1 Analysis Sets

Evaluable patients: patients who meet all of the protocol inclusion/exclusion criteria and begin treatment with the protocol regimen.

Safety set: data from all evaluable patients who receive initial treatment of the study treatment will be used in the analysis of safety.

Efficacy set: data from all evaluable patients who receive initial treatment of the study treatment will be used in the analysis of efficacy endpoints.

Exploratory set: the data from all study-eligible patients (i.e. those meeting all of the protocol inclusion/exclusion criteria) who begin the study treatment and have tissue samples taken will be used in the analyses to address the correlative biomarker aims.

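### The efficacy set holds only patients who reach olaparib, and the primary event has no rule for therapy without olaparib or for death, so the primary result does not describe everyone who waits

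*Combined protocol and SAP*

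**What the plan says.** Section 13.3.1 defines evaluable patients as "patients who meet all of the protocol inclusion/exclusion criteria and begin treatment with the protocol regimen" and builds the efficacy set from them: "Efficacy set: data from all evaluable patients who receive initial treatment of the study treatment will be used in the analysis of efficacy endpoints". It offers no other set for efficacy, and section 13.3.4 names none.

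Patients enrol within 8 weeks of finishing platinum (section 5) and then wait: "Olaparib treatment will be started when CA125 rises by two-fold of their nadir value" (section 6.1). The primary endpoint in section 1.1 is "The time from completion of platinum-based therapy for treatment of recurrence until initiation of post-olaparib treatment". PFS and OS run from enrolment (sections 1.2 and 14.1).

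During the wait, "Patients may undergo CT imaging prior to rise in CA-125 at the discretion of the treating physician for patient symptoms" (section 5). If other anticancer agents are needed, section 6.2.1 says: "If such agents are required for a patient then the patient must first be withdrawn from the study". The plan calls this neither an event nor a censoring. Death counts in PFS but is not mentioned for the primary endpoint, and section 13.3.4 gives no censoring rule.

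**The concern.** Entry to the efficacy set is decided by something that happens after the clock has started. Every analysed patient has, by construction, survived and stayed on study until CA-125 doubled.

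Two kinds of patient are lost, and they pull in opposite directions:

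- those who fail or leave before doubling; dropping them lengthens the analysed time to next therapy;
- those still untriggered at cut-off; dropping them shortens it.

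The rationale (section 2.4) asks whether waiting is better, or at least no worse, than immediate maintenance. An estimate restricted to those who completed the wait does not answer that.

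The event definition adds a second gap. Therapy given without olaparib is not post-olaparib treatment, and a death before next therapy has no stated handling. Two analysts could treat such patients differently and report different medians from the same data. The Study 19 PFS used as the benchmark counts progression or death (section 13.2), so the comparison is also not like for like.

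**Working it through.** **1. The plan's sample size.** Inputs from section 13.2: medians 8 and 11 months, one-sided level 0.10, power 90%, 24 months' accrual plus 18 months' follow-up.

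- Hazards: ln2/8 = 0.0866 and ln2/11 = 0.0630.
- Event probability with uniform accrual, 1 − [exp(−18λ) − exp(−42λ)]/(24λ): 0.912 and 0.834.
- N = [(1.2816 × 0.0866/√0.912 + 1.2816 × 0.0630/√0.834)/(0.0866 − 0.0630)]² = 75.1. The stated 75 reproduces.
- 75 × 1.10 = 82.5, hence about 83. The 10% is for loss to follow-up; nothing is allowed for never starting olaparib.

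**2. Who is in, and what counts.**

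| Course after enrolment | In efficacy set? | Primary event defined? |
|---|---|---|
| CA-125 doubles, olaparib, then another therapy | Yes | Yes |
| CA-125 doubles, olaparib, then death before another therapy | Yes | No rule |
| Other anticancer therapy before doubling | No | No: not post-olaparib |
| Death before doubling | No | No rule |
| Still untriggered at cut-off | No | No rule |

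Patients with lesions on the CT done at doubling are not the problem. Section 5 says "In the setting of new or progressive lesions, patients will be followed per protocol", so they may still start olaparib and stay in the set.

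**3. Size in a two-phase model.** The shares are assumptions. X is time in surveillance, exponential with median 3.7 or 4.8 months (the Study 19 placebo figures in section 13.2) or 6 (assumed). With probability f the patient fails at X; otherwise the event comes at X + Y. Y is exponential and is solved so that all-enrolled survival at 8 months is exactly 0.5 (for f = 10%, Y medians 3.31, 2.28 and 1.40). The analysis drops surveillance failures and anyone with X beyond cut-off. There are 83 enrolled, and cut-off is uniform on 18 to 42 months. The tests are:

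- exponential: z = [log(D/PT) − log(ln2/8)]√D;
- one-sample log-rank: z = (D − E)/√E, with the true all-enrolled curve as reference, an idealised case.

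Both reject below −1.2816. The table gives results for f = 5/10/15%:

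| X median | Treated-only median | Log-rank size, treated-only | Mean number analysed |
|---|---|---|---|
| 3.7 | 8.2/8.4/8.7 | 0.09/0.14/0.21 | 78.2/74.2/70.0 |
| 4.8 | 8.0/8.2/8.4 | 0.03/0.05/0.07 | 77.2/73.1/69.1 |
| 6 | 7.7/7.8/7.9 | 0.004/0.005/0.009 | 75.5/71.6/67.6 |

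Log-rank size for all enrolled is 0.09. The named exponential test rejects in under 1% of runs with either set, because two-phase times are not exponential.

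**4. Cut-off at 18 months for everyone**, one reading of footnote M in section 11. The untriggered share is 2^(−18/median) = 3.4, 7.4 and 12.5%. Treated-only medians are 7.0 to 8.5, below 8 in 7 of 9 cases.

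**5. Exponential times, the plan's own assumption.** All enrolled have median 8. A share f fail in surveillance at exponential times (median 3.7 or 4.8), and starters trigger at half, or at a uniform fraction, of their event time. The named test has size 0.09 on all enrolled. Treated-only, the size is 0.04 to 0.22 (medians 7.9 to 9.0) with cut-off at 18 to 42 months, and 0.01 to 0.10 (medians 7.4 to 8.5) with 18 months for all.

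**6. Deaths**, if 5% or 10% of failures are deaths and are censored (all enrolled, f = 10%). Two-phase medians become 8.3 or 8.6 to 8.7, and the named test stays within its level (0.001 to 0.03, or 0.01 to 0.09). On an exponential curve the median becomes 8/0.95 = 8.42 or 8/0.90 = 8.89, and the size 0.19 or 0.33.

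**The case against.** **The set could be read more widely.** The words protocol regimen might include surveillance. But the efficacy set also requires receipt of study treatment, in the same wording as the safety set, and section 12.1.1 ties treatment to olaparib: "All patients will be evaluable for toxicity from the time of their first treatment with olaparib". At best the text is ambiguous about who is in the primary analysis.

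**The effect may be small.** This stands in part. No surveillance-failure share is given. The trigger has no stated minimum level and no confirmation sample, which suggests few non-starters. At 5% with the Study 19 placebo medians, the two-phase treated-only medians are 8.0 to 8.2, and under exponential times with cut-off at 18 to 42 months the named test's size is 0.04 to 0.09. Section 2.4 says CA-125 is elevated in over 90% of advanced cases, but that is not the share who start olaparib. The 0.21 needs a 15% failure share and the fallback test. The result also depends on the removal rule: if those dropped are drawn from events before 4.8 months on an exponential curve, size is 0.17 at 5% and 0.28 at 10%.

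**The 18-month reading deserves little weight.** This stands: sections 13.2 and 13.3.4 place the analysis 18 months after the last accrual.

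**The number analysed may be safe.** Section 13.2 can be read as accruing until 75 have started olaparib. That protects the number but leaves the selection in place.

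**The event is not wholly undefined, and deaths may be few.** The objective in 1.1 speaks of first subsequent therapy, which is broader than its endpoint. Eligibility requires life expectancy over 6 months, and Study 19 median OS was 27.8 to 29.8 months. Censoring deaths would be a possible rule, but the plan states none.

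**Conclusion.** The concern holds and must be fixed before analysis. As written, the primary estimate is conditioned on a post-enrolment event, and the primary event has no rule for therapy without olaparib or for death. This follows from the text and needs no simulation.

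The size is uncertain because every share is assumed. With the section 13.2 medians and 5 to 10% failing in surveillance, the two-phase treated-only median is 8.0 to 8.4 against a true 8. Wider assumptions move the median and the test size either way. With 83 enrolled, 10% or 15% early non-starters leave about 72 to 74 or 68 to 70 analysed, below 75 before any loss to follow-up; at 5% the number stays above 75.

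One limit: analysing all enrolled does not restore the level of the named exponential test when times are two-phase. That is a separate weakness of the test.

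**What to change.** - **Section 13.3.1:** for time to next therapy, PFS and OS, define the efficacy set as all eligible enrolled patients, whether or not olaparib was started.
- **Sections 1.1 and 14.1:** define the primary event as the first anticancer therapy other than protocol olaparib, or death from any cause; censor others at last contact. Make the synopsis agree, and also sections 6.4 and 6.6, where follow-up or time on study ends at post-olaparib therapy.
- **Olaparib-treated set:** keep it for safety, response and PK.
- **Reporting:** give treated-only efficacy as a sensitivity analysis, with counts of non-starters by reason (died, other therapy, withdrawn, not yet triggered).

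The cost is a protocol and SAP amendment, because the primary endpoint text changes. The team must confirm that next-therapy and death dates are captured for non-starters. Section 6.4 already plans at least 18 months of follow-up from enrolment whatever the reason for removal, but withdrawal of consent ends it (section 6.5). The reported median may become less favourable. No extra patients are needed, since non-starters then count.

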13.3.2 Analysis of Baseline Demographic Variables

Baseline descriptive statistics on all evaluable patients will be provided for demographic variables (age, BMI, race/ethnicity), ECOG performance status, disease stage and status at the time of enrollment (stable disease, progressive disease), and treatment regimens previously used.

13.3.3 Analysis of Safety Endpoints

The NCI common terminology criteria for adverse events (CTCAE 5.0) will be used to evaluate toxicity; we will consider a toxicity to be an adverse event that is possibly, probably or definitely related to treatment. The maximum grade of toxicity for each category of interest will be recorded for each patient and the summary results will be tabulated by category and grade. Statistics on the number of cycles received by patients and any dose reductions will also be tabulated.

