1.2. Secondary Objectives and Endpoints

- 1.2.1. To estimate the progression-free survival (PFS) for delayed start olaparib in platinum sensitive recurrent epithelial ovarian cancer with a complete or partial response to last platinum therapy
 - 1.2.1.1. Endpoint: PFS defined as time from enrollment until detected recurrence or progression of disease, via RECISTv1.1, or death from any cause
- 1.2.2. To estimate the overall survival (OS) for delayed start olaparib in platinum sensitive recurrent epithelial ovarian cancer with a complete or partial response to last platinum therapy
 - 1.2.2.1. Endpoint: OS defined as time from enrollment until death from any cause
- 1.2.3. To determine the safety and tolerability for delayed start olaparib in platinum sensitive recurrent epithelial ovarian cancer with a complete or partial response to last platinum therapy
 - 1.2.3.1. Endpoint: Toxicity rates defined by the National Cancer Institute's Common Terminology Criteria for Adverse Events (CTCAE) v5.0
- 1.2.4. To determine the overall response rate of delayed start olaparib in platinum sensitive recurrent epithelial ovarian cancer with a partial response or complete response to last platinum therapy stratified by BRCA mutational status
 - 1.2.4.1. Endpoint: Overall response rate as defined by RECIST v1.1
- 1.2.5. To evaluate the impact of delayed start olaparib in platinum sensitive recurrent epithelial ovarian cancer with a complete or partial response to last platinum therapy on patient reported adverse events
 - 1.2.5.1. Endpoint: Patient reported adverse events as reported by the NCI Patient Reported Outcomes-Common Terminology Criteria for Adverse Events (PRO-CTCAE)
- 1.2.6. To evaluate the impact of delayed start olaparib in platinum sensitive recurrent epithelial ovarian cancer with a complete or partial response to last platinum therapy on quality of life

- 1.2.6.1. Endpoint: Health-related quality of life measured via The Functional Assessment of Cancer Therapy + Ovarian-specific scale (FACT-O)
- 1.2.7. To evaluate the impact of delayed start olaparib in platinum sensitive recurrent epithelial ovarian cancer with a complete or partial response to last platinum therapy on physical functioning
 - 1.2.7.1. Endpoint: Physical function assessed through the PROMIS Physical Function-20a assesses self-reported performance of physical activities

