8.2 Adverse Event Characteristics

- **CTCAE term (AE description) and grade:** The descriptions and grading scales found in the revised NCI Common Terminology Criteria for Adverse Events (CTCAE) version 5.0 will be utilized for AE reporting. All appropriate treatment areas should have access to a copy of the CTCAE version 5.0.
- **Attribution** of the AE:
 - Definite The AE *is clearly related* to the study treatment.
 - Probable The AE *is likely related* to the study treatment.
 - Possible The AE *may be related* to the study treatment.
 - Unlikely The AE *is doubtfully related* to the study treatment.
 - Unrelated The AE *is clearly NOT related* to the study treatment.

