8.4 Routine Adverse Event Reporting

All Adverse Events **must** be reported in routine study data submissions.

Adverse event data collection and reporting, which are required as part of every clinical trial, are done to ensure the safety of patients enrolled in the studies as well as those who will enroll in future studies using similar agents. AEs are reported in a routine manner at scheduled times during the trial.

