13.3.4 Analysis of Efficacy Endpoints

Allowing 18 months of follow-up following the last patient accrual, time to next treatment will be estimated by the Kaplan-Meier method. Median time to next treatment will be estimated with 90% confidence intervals. The maximum likelihood estimate of the hazard rate (hazard of next treatment) will be calculated and used to conduct a one-tailed

exponential test at level alpha = .10. This will test the hypothesis that time to next treatment is increased over that expected for olaparib without delay (this assumes the data follow an exponential distribution, otherwise, an alternate parametric test or a one sample log rank test will be used). Toxicities will be summarized by grade, frequency and attribution to olaparib. Median progression-free survival (PFS) and overall survival (OS) will be estimated using the Kaplan Meir method. The Kaplan-Meier method with a log rank test will be applied to test differential response by mutation status. We will estimate the response rate utilizing RECIST and/or GCIG criteria. For those patients with measurable disease and elevated CA125, both RECIST and GCIG criteria will be utilized. For those without measurable disease, GCIG criteria alone will be used to record response. Overall response will be defined as the number of patients with best overall response of CR and PR. The effect of treatment will be reported with its supporting 90% confidence interval.

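### The clinician-graded safety table is limited to events judged related to olaparib, and no all-cause or serious-event table is clearly planned beside it.

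*Combined protocol and SAP*

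**What the plan says.** The safety endpoint is stated in section 1.2.3 as "Toxicity rates defined by the National Cancer Institute's Common Terminology Criteria for Adverse Events (CTCAE) v5.0", and section 14.1 repeats it in the same terms. Neither place makes relatedness to treatment a condition.

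The condition enters in section 13.3.3: "we will consider a toxicity to be an adverse event that is possibly, probably or definitely related to treatment". The table follows from that definition: "The maximum grade of toxicity for each category of interest will be recorded for each patient", with results laid out by category and grade.

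One further sentence, placed in the efficacy section (13.3.4), reads "Toxicities will be summarized by grade, frequency and attribution to olaparib".

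On collection, section 8.2 grades attribution on five levels. The lowest two are *unlikely*, for an event that "is doubtfully related" to the study treatment, and *unrelated*, for one that "is clearly NOT related" to it. Section 8.4 says that all adverse events must "be reported in routine study data submissions", and that "AEs are reported in a routine manner at scheduled times during the trial".

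**The concern.** Safety and tolerability is a secondary objective, and sparing patients toxicity is part of the rationale for delay in section 2.4. The trial is single-arm and open-label (section 5). No comparator rate exists against which attribution can be judged, and whoever assigns it knows that the patient is on olaparib. That this is the investigator is a reasonable inference; section 13.3.3 does not say.

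If the only clinician-graded table keeps related events, a reader of the results cannot see how many events were set aside or recover the all-cause rate. Three other parts of the protocol make this matter:

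- Section 6.3 defines the unacceptable adverse event that ends treatment without a relatedness condition in that definition. A patient could stop for an event scored *unlikely* and have no entry for it in the safety table.
- Section 8.3.1 requires deaths to be reported whatever their cause, but the planned table has no place for those judged unrelated.
- Section 10.1.6 compares olaparib trough concentrations between patients with and without toxicity. If the 13.3.3 definition applies there, attribution error carries into that comparison.

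**Working it through.** The plan states no toxicity rate, threshold or precision target, so there is no figure to reproduce. The check is a reading of the sections against each other.

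**1. What enters the 13.3.3 table.** Section 8.2 has five levels: definite, probable, possible, unlikely, unrelated. The definition admits the first three. So 3 of 5 levels enter and 5 − 3 = 2 do not.

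**2. Whether the excluded events are recorded.** Section 8.4 requires all adverse events in routine submissions, and section 8.2 makes attribution one of the recorded characteristics. The data for an all-cause table will exist.

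**3. Whether 13.3.4 restores them.** There are two readings.

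| Meaning of toxicities in 13.3.4 | What the attribution breakdown covers | All-cause rate recoverable? |
|---|---|---|
| As defined in 13.3.3 | Possible, probable, definite | No |
| Any adverse event | All five levels | Counts yes, but one word then has two meanings in adjacent sections |

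The first reading is the natural one, because the definition stands in the section just before. The second cannot be excluded. The supportable statement is that no all-cause tabulation is clearly specified.

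**4. Whether another section supplies the table.** Section 13.3.5 analyses patient-reported adverse events with longitudinal mixed models and no attribution filter. Its data are the PRO-CTCAE items in Appendix D. These include nausea (item 5), abdominal pain (item 11) and fatigue (item 25). They do not include laboratory events such as anemia or neutropenia, or diagnoses such as myelodysplastic syndrome, all of which section 8.1 lists for olaparib. The analysis is also of scores over time, not of maximum-grade incidence. No section of the analysis plan describes a table of serious adverse events.

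**5. What can be said about direction.** For one event category, let A be the proportion of patients with any such event, R the proportion with at least one scored possible or higher, and D the proportion with at least one truly caused by olaparib. Then

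- R ≤ A, always, because the related events are a subset;
- R − D = (share counted in R but not in D) − (share counted in D but not in R).

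The first term is over-attribution and the second is under-attribution. The documents give neither, so the sign and size of R − D cannot be derived. The certain statement is that R cannot exceed A, and that the plan does not clearly call for A.

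**The case against.** The strongest reply is that attribution is not unchecked. PRO-CTCAE is collected before olaparib as well as during it (section 11), and section 13.3.5 looks for a change at drug start, with a knot at that time as one named option. For nausea, abdominal pain and fatigue this within-patient comparison separates drug from disease better than an all-cause incidence table would. That stands for the symptoms on the form. It does not reach laboratory, most serious or other events.

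A second reply is that confounding by relapse should be limited at the start of olaparib. Section 2.4 expects CA-125 to rise 3-5 months before disease is clinically evident, and treatment to begin before symptoms. That also stands for the start. Treatment continues to RECIST progression, so overlap may grow later.

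Third, the omission is recoverable: all events are recorded, serious events go to the sponsor whatever their attribution (section 8.3.1), safety is reviewed monthly (section 13.2.1), and no test or stopping boundary uses the table. This is correct and limits how serious the point is. It also shows how little the remedy costs.

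Two stronger readings are tempting and are not supported. A reader might infer that all-cause events will never be tabulated; the ambiguity of the 13.3.4 sentence does not allow that. A reader might also infer that the reported rates are biased downwards, and size the bias by applying an assumed share of misattributed events to the incidences in section 8.1. But *possible* is an inclusive threshold, and an unblinded assessor who knows olaparib's listed effects may over-attribute. Section 8.1 does not say whether its figures are all-cause or drug-related, and its 67% for fatigue is an upper bound. The documents give no misattribution rate.

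**Conclusion.** The point holds as a gap in the safety reporting plan. Section 13.3.3 narrows an endpoint that carries no relatedness condition to 3 of the 5 attribution levels, and no section clearly specifies an all-cause CTCAE table or a serious-event table. The clinician-graded toxicity rates therefore rest on unblinded attribution with no control arm. The resulting error may go either way, and its size cannot be estimated from the documents.

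This rests on reading toxicities in 13.3.4 as 13.3.3 defines the word. If the sponsor meant all adverse events there, all-cause counts would be available and the remaining fault is inconsistent terminology, which the same edit cures. The time-to-next-therapy analysis, its alpha and its power do not depend on this. The change is worth making because it is specific and cheap and lets readers see both rates, not because a bias has been shown.

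**What to change.** In section 13.3.3:

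- Make the main safety table the highest CTCAE grade per patient, by category, for all adverse events from the first olaparib dose, whatever their attribution.
- Add a table of serious adverse events on the same basis.
- Keep the possible, probable and definite subset as a second table, presented with the first.

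In section 13.3.4, replace toxicities with adverse events, and state that the summary by grade and frequency covers all five attribution levels. In section 10.1.6, say which definition of toxicity the exposure comparison uses.

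The cost is a few sentences of wording and one or two extra tables from data already collected with attribution. The drawback is that all-cause rates will include events due to the disease and, without a control arm, would overstate drug toxicity if read alone. That is why the two tables should appear together.
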